##### Adequate Clinical and Parasitological Response

- Absence of parasitemia on study Day 42, with no prior requirement for additional treatment other than the standard 6 dose regimen received at time of presentation with malaria.

- For subjects who experience treatment failure before study Day 3, PK sampling will be discontinued.

Participants from TDH or MGH who experience recurrent malaria within 42 days will be evaluated for reenrollment eligibility (see Section 4.1 and 4.2). If eligible, they will be re-enrolled into the appropriate study. For those not eligible or not willing to reenroll, effort will be made to follow them for 7 days (or longer if they remain sick) after the diagnosis of recurrent malaria. In addition, the most recent laboratory and clinical tests will be checked to assess for any grade 3 or 4 abnormalities. If present, repeat testing should be done until AE is resolved.

In the case of participant withdrawal (unless a participant cannot be located or refuses follow-up), attempt will be made to follow them until all AEs are resolved to grade 2 or below, AND until Day 7 of follow-up for treatment of current malaria episode. Attempt will also be made to obtain the Day 14 hematology and chemistry blood work for safety follow-up.

## **6.5 Anthropometric measurements to assess nutritional status.**

All children will have nutritional status characterized at enrollment based on assessment of WHO 2009 growth indicators by staff trained in the proper assessment of growth measurements. Specifically, measurements for height, weight, age and mid-upper-arm circumference (as a proxy for “weight for height, WFA”) will be collected and recorded at the time of first enrollment (for the first PK assessment around an episode of uncomplicated malaria) and at the time of each subsequent episode of uncomplicated malaria for which children will also undergo PK.

## **6.6 Clinical Laboratory Studies**

Blood will be collected on Study Day 0, 14, and 28 for CBC, differential, liver function tests (LFTs; AST, ALT). Additional venipunctures may be performed, as appropriate, for laboratory testing to evaluate non-malarial medical illnesses at the discretion of study physicians. Results will be made available to study physicians for patient management decision-making. HIV-infected children will have baseline CD4 and VL testing performed.

HIV-uninfected children will have HIV serostatus documented through rapid testing. All positive test results generated for the purpose of this study will be confirmed through Western Blot or HIV RNA. If needed, HIV counseling and referral will be made. Children will not be notified of HIV testing results. Parents and guardians will be notified, and provided post-test counseling, and referred to the appropriate HIV clinic for care. HIV infected children will be expected to have HIV status confirmed through their clinic and will be required to be stabilized on at least 10 days of EFV-based ART to meet enrollment criteria.

## **6.7 Pharmacology Laboratory Studies**

### **6.7.1 Intensive pharmacokinetic study**

For children participating in the intensive PK sampling, Coartem® treatment will be on Study Days 0, 1, 2 and 3 (for the 6-dose regimen) or Study Days 0,1,2,3,4 and 5 (for the 10-dose regimen). Intensive PK samples for AL (artemether, DHA, and lumefantrine) will be collected on Study Day 3 or 5, around the 6th or 10th (i.e. last) treatment dose for all subjects enrolled in the study. AL administration of the 6th or 10th dose will be observed in the clinic, as well prior morning doses. In addition, two samples will be collected on Study Days 0, 1 and 2 (for those randomized to 3-day AL) or on Study Days 0, 1, 2, 3 and 4 (for those randomized to 5-day AL).

### **Sampling for artemether, dihydroartemisinin and lumefantrine.**

*Capillary* samples (200 µL each\*) will be collected by finger stick at approximately 2 and 4 hours post- each morning AL dose. A pre-1st dose sample will also be collected to confirm no residual antimalarial drug is detectable. On Study Day 1 (when a single dose is administered mid-day) capillary samples will also be collected at approximately 2 and 4 hours post- this dose.

Intensive *venous* sampling will occur via an indwelling catheter prior to and 0.5 1, 2, 3, 4, 6 and 8 hours post-administration of the 6th or 10th dose (for the 3-day and 5-day AL regimens, respectively) for the determination of artemether, DHA, and lumefantrine concentrations in plasma (500 µL each\*). Participants will remain in the clinic until completion of the 8-hour blood sampling on Study Day 3 or 5 (for the 3-day and 5-day AL regimens, respectively) and discharged home. They will then return to the clinic the next morning for the 24-hour sample.

To determine the correlation between capillary and venous artemisinin exposure, a simultaneous capillary sample (200 µL) will be collected at the time of the 2 and 8-hour samples.

### **Sampling for lumefantrine**

Participants will be asked to return to the clinic on Study Days 8, 14, and 21 (*venous or capillary* sampling, 200 µL each).

PK sampling will be discontinued in patients who do not meet laboratory eligibility criteria or do not complete treatment due to early failure. Subjects with repeat malaria infection during the 42-day follow-up will provide an additional PK sample and blood smear.

\*200 µL *capillary* samples will be collected by finger prick and can be used to measure all 3 analytes but without the ability to do repeat analysis if necessary. 500µL *venous* samples permits repeat analysis as needed.

## **6.7.2 Population pharmacokinetic study**

For children participating in the population PK sampling, AL treatment will be 6 or 10 doses of Coartem® (provided by the study) administered over 3 or 5 days: Study Days 0, 1, and 2 or Study Days 0,1,2,3 and 4, *Capillary* samples for lumefantrine only (200 µL) will be collected on Study Day 0 (prior to AL administration). *Capillary* samples for artemether/DHA and lumefantrine (200 µL\*) will be collected by finger prick on Study Days 0-2 (3 day AL) or 0-4 (5 day AL) at approximately 2 and 4 hours post-dose. In a subset of children, *capillary* samples for artemether/DHA and lumefantrine (200 µL\*) will be collected by finger prick on Day 2 in the 3-Day regimen and on Day 4 in the 5-Day regimen, prior to AL administration. On Study Days 3 (3 day AL) or 5 (5 day AL) at approximately 24 hours post-last dose, an additional capillary sample will be taken. In addition, *capillary or venous* samples will be collected for lumefantrine only on Study Days 7, 14, 21. Subjects with repeat infection during the 42-day follow-up will provide an additional PK sample at the time of repeat infection.

\*200 µL *capillary* samples will be collected by finger prick and can be used to measure all 3 analytes but without the ability to do repeat analysis if necessary. 500µL *venous* samples permits repeat analysis as needed.

### **6.7.3 PK Sample collection and handling**

For consistency, blood samples will be obtained from capillary or venous sources, as specified. However, if venous PK samples cannot be obtained at desired times due to technical or other limitations, technicians may obtain blood from a capillary site. Prior correlation studies between venous and capillary measurements for lumefantrine have confirmed the ratio of concentrations is 1:1. For the artemisininis, correlation studies will be carried out in the context of this protocol.

All samples will be immediately placed on dry ice, processed for plasma, transferred to liquid nitrogen, and shipped at a later date on dry ice to our laboratory for analysis. Liquid nitrogen will be obtained from Kampala.

### **6.7.4 Assays for artemether, DHA and lumefantrine**

Artemether, DHA and lumefantrine and active desbutyl-lumefantrine will be measured using optimized methods validated in our laboratory. All methods will utilize liquid chromatography tandem mass spectrometry.

## **6.8 Parasitology Laboratory Studies**

**Thick blood smears.** Parasite counts (asexual stage and gametocyte counts) via blood smears will be collected in all participants on each day of clinical follow-up. In addition, in a subset of population PK participants, more frequent thick blood smears will be collected to document the rate of parasite clearance, as we have done in prior studies.

Thick blood smears will be stained with 2% Giemsa and read by experienced laboratory technologists who are not involved in direct patient care. Parasite densities will be calculated by counting the number of asexual parasites per 200 leukocytes (or per 500 leukocytes, if the count is <10 asexual parasites/200 leukocytes), assuming a leukocyte count of 8,000/ $\mu$ L. A blood smear will be considered negative when the examination of 100 high power fields does not reveal asexual parasites. Gametocytemia will also be determined by thick blood smears. At varied time points, blood smears for the determination of parasitemia will be obtained by simultaneous venous and capillary blood draws. Parasitology studies will be performed in the laboratory of [name] at Yale School of Public Health

**LAMP** will be done using a commercially available DNA amplification kit (such as the Loopamp Plasmodium Kit, Eiken, Japan). LAMP will be performed on dried blood spot specimens during each day of 42-day follow-up (See SOE). All LAMP will be run at our laboratory on the TDH clinic or Yale by those trained in LAMP.

**Rapid Diagnostic Test.** The Alere™ Malaria Ag P.f., will be prepared and used per manufacturer's instructions ([www.alera.ecom/malaria-POC](http://www.alera.ecom/malaria-POC)). A drop of capillary whole blood obtained by finger prick will be placed onto the RDT well, along with control buffers, and read according product insert. The total time for preparation and resulting is estimated at 20 minutes.

**Molecular studies.** Parasite genotyping using polymorphic markers will be conducted to assess genetic diversity using methods routine in our laboratory to determine the multiplicity of infection (MOI). Six polymorphic markers (merozoite surface protein (MSP)-1, MSP-2, and 4 microsatellites) will be typed using capillary electrophoresis. For drug resistance genotyping, extracted DNA will be amplified by PCR, and following amplification, multiplex LDR will be conducted with bead-specific oligonucleotides, followed by hybridization to magnetic beads, and fluorometric assessment of mutation prevalence on a Bio-Plex system (Bio-Rad, Hercules, CA). RNA-based studies will also be performed for more sensitive detection of asexual blood stages and gametocytes. RNA-based studies will allow for the most sensitive quantification of parasite and gametocyte clearance between study regimens, as well as early detection of recurrent parasitemia.

**Metabolomics studies.** Metabolomics assays will be conducted using plasma and/or RBC pellets. 20 $\mu$ L of plasma will be placed in an ice-cold methanol solution, vortexed, and stored in -80°C. De-identified metabolomics study samples will be shipped on dry ice to the lab of [name], an expert in malaria metabolomics, at Monash University for analysis.

## 6.9 Blood volumes

### **Intensive PK study**

The total blood volumes collected from intensive PK study participants during the 42-day follow-up period for single episode of malaria will be no more than 28 mL (~6 teaspoons). (Section 11.1).

### **Population PK study**

The total blood volumes collected from participants in the population PK study during the 42-day follow-up period for each malaria episode will be approximately 21 mL (~4-5 teaspoons). (Section 11.1)

RNA and Metabolomic studies will not be performed in those under 10kg to assure blood volumes are not excessive in this weight range.

### **6.10 Electrocardiogram (ECG) monitoring**

As noted in section 7.2, AL has an excellent safety profile. It was first registered as Coartem® in 1998, and is used in over 90 countries worldwide, including the U.S. In 2016, the WHO convened an Evidence Review Group (ERG) to assess the cardiac safety of antimalarials, with particular focus on the QT interval. Of note, members of the ERG noted that the QT interval is associated with the risk of drug-induced torsades de pointes (TdP), a potentially lethal arrhythmia. The review followed the “ICH E14: The clinical evaluation of QT/QTc interval prolongation and proarrhythmic potential for non-antiarrhythmic drugs”, guidelines set forth by the Food and Drug Administration (FDA). According to E14 guidelines, QT intervals should be corrected for heart rate, and Fridericia’s correction is considered sufficient ( $QTc = QT/RR^{0.5}$ ). In addition, an increase in QT or  $QTc > 500ms$  or  $>60ms$  above baseline are considered thresholds of particular concern. Categorical analysis and AE reporting are also recommended with absolute QT/QTc intervals of  $>450$ ,  $>480$ , and  $>500$ , or increases of  $>30ms$ , and  $>60ms$  above baseline.

According to the review, no cases of sudden or unexplained cardiac death have been reported with AL up to the time of the ERG. Despite *in vitro* evidence of inhibition of hERG currents, which are associated with QT interval prolongation, no QTc interval prolongation was seen *in vivo* in dogs with AL, except at doses of 600mg/day, far exceeding the doses being administered in this study. In a thorough QT study, an increase of  $>10ms$  was excluded. In clinical trials, no pediatric patients aged  $<12$  years had a post-baseline QTcF interval of  $>500ms$ , while 0.2% of the adult patients reported an interval of  $>500ms$ . In conclusion, the committee stated that “The small increase in QTc interval associated with AL does not appear to be associated with a significant risk of arrhythmia. The small number of adverse events affecting the cardiovascular system were almost all of mild intensity and resolved without intervention.”

In order to confirm the expected safety of an extended dosing regimen of AL, we will conduct ECGs in a sub-set of up to 50 children in each arm (3-Day and 5-Day) prior to the administration of the first dose of Coartem®, at the time of expected  $C_{max}$  (maximum concentration), and at 2 time-points following recovery from malaria. ECGs will be performed in triplicate, with the average QTc (central tendency) used for analyses. Based on prior data from our group, the time of expected maximum concentration is 4-6 hours following the last dose of AL. ECGs are feasible at this time in the intensive study. However, due to the last dose occurring in the evening of day 2 or 4 in population PK participants, ECGs will only be performed on the morning of day 3 or 5 in the population PK arm, corresponding to an estimated 8-14 hours post-last dose.

Specifically, ECGs will be performed in up to 50 participants in each arm (3-Day and 5-Day) at the following time points:

- **Intensive PK study**
  - 3- day regimen
    - Day 0 – baseline, prior to the 1st dose of AL
    - Day 3 – prior to the last dose, and 4 to 6 hours after the last dose
    - Day 8
    - Day 28 or later
  - 5- day regimen
    - Day 0 – baseline, prior to the 1st dose of AL
    - Day 5 – prior to the last dose, and 4 to 6 hours after the last dose
    - Day 8
    - Day 28 or later
- **Population PK study**
  - 3- day regimen
    - Day 0 – baseline, prior to the 1st dose of AL
    - Day 3 – 8-12 hours after the last dose
    - Day 7
    - Day 28 or later
  - 5- day regimen
    - Day 0 – baseline, prior to the 1st dose of AL
    - Day 5 – 8-12 hours after the last dose
    - Day 7
    - Day 28 or later

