## GLOSSARY

ACT	Artemisinin-combination therapy
AE	Adverse event
AL	Artemether-lumefantrine
ALT	Alanine transaminase (SGPT)
ART	Antiretroviral therapy
AS/AQ	Artesunate-amodiaquine
AST	Aspartate aminotransferase (SGOT)
AUC	Area under the curve
BID	Twice a day
CAB	Community Advisory Board
CBC	Complete blood count
CDC	Center for Disease Control
CI	Confidence Interval
C max	Maximum plasma concentration of a drug
C min	Trough serum concentration of a drug
Cr	Creatinine
CRF	Case report form
CYP3A4	Cytochrome p450 3A4
CYP2B6	Cytochrome p450 2B6
DAIDS	Division of AIDS
DHA	Dihydroartemisinin
DMC	Data Management Centre
DP	Dihydroartemisinin-piperaquine
DSMB	Data and Safety Monitoring Board
ECG	Electrocardiogram
EFV	Efavirenz
H	Hour
HFA	Height for age
Hg	Hemoglobin
HIV	Human Immunodeficiency Virus
HRPP & IRB	Human Research Protection Program and Institutional Review Board
HS-RDT	High sensitive rapid diagnostic test
IDRC	Infectious Disease Research Center
IPT	Intermittent preventive therapy (for malaria)
IRB	Institutional review board
ITN	Insecticide treated net
LAMP	Loop-mediated isothermal amplification
LBW	Low birth weight (<2500g)
LPV	Lopinavir
LPV/r	Lopinavir/ritonavir
LR	Lumefantrine
MGH	Masafu General Hospital
MOH	Ministry of Health
MU	Makerere University

NDA	Uganda National Drug Authority
NICHHD	National Institute of Child Health and Human Development
NIH	National Institutes of Health
NLME	Non-linear mixed effects
NNRTI	Nonnucleoside reverse transcriptase inhibitor
NRTI	Nucleoside reverse transcriptase inhibitor
NVP	Nevirapine
OR	Odds ratio
PCR	Polymerase chain reaction
PD	Pharmacodynamics
PI	Protease inhibitor
PK	Pharmacokinetics
PO	Oral
PQ	Piperaquine
PROMOTE	Prevention of Malaria and HIV Disease in Tororo
Q	Every
QTc	Corrected QT interval
QTcB	Corrected QT interval using Bazzett's correction
QTcF	Corrected QT interval using Fridericia's correction
QD	Once every day
RR	Relative Risk
SD	Single dose
SP	Sulfadoxine-pyrimethamine
TASO	The AIDS Support Organization
TDH	Tororo District Hospital
TS	Trimethoprim-sulfamethoxazole
UCSF	University of California, San Francisco
ULN	Upper limit of normal
UNAIDS	Joint United Nations Program of HIV AIDS
UNCST	Ugandan National Council for Science and Technology
WFA	Weight for age
WFH	Weight for height
WHO	World Health Organization

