## 9.0 STATISTICAL CONSIDERATIONS

### 9.1 General Design Issues.

This is a prospective study to evaluate the PK and PD of extended dose AL in the context of EFV-based ART and in the context of HIV-uninfected children and to characterize the impact of a 5-day regimen on AL PK/PD as compared to the standard 3-day regimen; the study will be conducted in Uganda.

The current proposal will study the PK/PD of AL in HIV-infected children on EFV-based ART and HIV-uninfected children not on ART either enrolled at TDH or MGH. We will compare the PK of 5-day AL in HIV-infected children on EFV-based ART to 1) 3-day AL in HIV-infected children on EFV-based ART, and 2) 3-day AL in HIV-uninfected children. In addition, we will compare the PK of 5-day AL in HIV-uninfected children to 3-day AL in HIV-uninfected children. Comparisons will be based on an intensive PK design for AL AUC estimations in 30 to 50 subjects for each of the study groups. Study group comparisons will be controlled for age (i.e. results for HIV infected children on EFV-based ART who are 3-10 years of age, will be compared to results for HIV uninfected children who are also 3-10 years of age). The proposal will also study the impact of AL exposure on treatment outcomes and adverse events using a population PK/PD design. This will involve population PK study of up to an additional 100 HIV-infected children and 120 HIV-uninfected children.

*Although an individual child is eligible to enroll in both the intensive PK study and the population PK study for separate episodes of malaria, there is no assurance that the same child will contribute to both study components. Thus, it is possible that the total number of subjects for all groups may be as high as 380.*

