#### 9.2.2 Secondary outcomes

- 1) Safety of 5-day vs 3-day AL regimens
- 2) Prevalence of gametocytemia following treatment in 3-day vs 5-day AL regimens
- 3) Weight-for-age and Height-for-age associations with PK
- 4) Diagnostic sensitivity of LAMP, HS-RDT, and microscopy for the detection of recurrent parasitemia.
- 5) Metabolomic measurements in HIV infected vs HIV uninfected children
- 6) Relationship between molecular markers of drug resistance and treatment failure

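### Section 6.10 cites QTc thresholds without committing to count children who cross them, Section 9 gives no method for the implied 5-day v 3-day QTc comparison, and the Fridericia formula is printed with exponent 0.5

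*Combined protocol and SAP*

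**What the plan says.** Section 6.10 gives the purpose of the ECGs: "In order to confirm the expected safety of an extended dosing regimen of AL". Up to 50 children in each regimen arm have ECGs before the first dose, around the end of treatment (Day 3 or Day 5), on Day 7 or 8, and on Day 28 or later. In the intensive study the end-of-treatment ECGs are before the last dose and 4 to 6 hours after it. In the population study the last dose is in the evening, so "ECGs will only be performed on the morning of day 3 or 5 in the population PK arm", listed as 8 to 12 hours after the last dose.

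The background paragraph of the same section summarises E14 guidance. It names QTc above 500 ms, or more than 60 ms above baseline, as the values to worry about, and continues: "Categorical analysis and AE reporting are also recommended with absolute QT/QTc intervals" above 450, 480 and 500 ms, and for increases above 30 and 60 ms. No sentence adopts these as study analyses. The only statement of what this study will do is "ECGs will be performed in triplicate, with the average QTc (central tendency) used for analyses".

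The same paragraph says that Fridericia's "correction is considered sufficient ( $QTc = QT/RR^{0.5", an exponent of 0.5. The Glossary has separate entries for QTcB and QTcF, the latter being "Corrected QT interval using Fridericia's correction", and Section 6.10 itself cites QTcF results.

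Section 9.2.2 lists "Safety of 5-day vs 3-day AL regimens" as a secondary outcome, matching the first secondary objective in Section 2.2. Section 9 contains no QTc endpoint, contrast, interval or table. Section 9.1 plans to study the "impact of AL exposure on treatment outcomes and adverse events using a population PK/PD design", which is an exposure analysis and not a regimen comparison of QTc.

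**The concern.** QT risk is carried by individual outliers, which is why the guidance that the protocol cites is framed in per-child cut-offs. An arm mean can stay almost flat while a few children cross them. As written, the team could report mean QTc alone, stay within the plan, and describe the result as supporting the safety of the 10-dose regimen. Whether outliers are reported, and how the regimens are compared, would be settled after the data are seen.

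The exponent adds a second problem. Children with acute malaria tend to have fast heart rates that fall with recovery. An exponent that is too large over-corrects at fast rates, most strongly on Day 0. It therefore inflates absolute QTc and shrinks the rise from Day 0, so both kinds of threshold count would be wrong if the formula were programmed as printed.

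**Working it through.** The plan gives no SD, margin, power or precision for the ECG subset, so there is no stated figure to reproduce. From the documents: 50 children per regimen (the maximum), the cut-offs, and the printed exponent 0.5. Everything marked assumed below is not in the documents.

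**1. Mean against count.** Suppose 2 of 50 children on 5-day AL rise by 70 ms and 48 do not change.
- Shift in the arm mean: 2 × 70 / 50 = 2.8 ms (one child gives 1.4 ms, three give 4.2 ms).
- 95% half-width for a 50 v 50 difference in means, t(0.975, 97) × SD × √(2/50): 6.0, 7.9 and 9.9 ms at assumed SD 15, 20 and 25 ms.
- Adjusted for a Day 0 QTc with assumed correlation 0.5, SD is multiplied by √(1 − 0.25): 5.2, 6.9 and 8.6 ms.
- The count shows 2/50 = 4%, exact 95% interval 0.5% to 13.7%.

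The shift lies well inside every half-width, so the mean would look unchanged while the count would not.

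**2. What zero events would exclude.** The one-sided 95% upper limit for 0/50 is 1 − 0.05^(1/50) = 5.8%; the two-sided limit is 1 − 0.025^(1/50) = 7.1%. The number with a 4 to 6 hour ECG is not stated. If it were 25 (assumed), 0/25 gives 11.3% one-sided.

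**3. Effect of the exponent.** If the true exponent is a and the programmed one is b, the computed value is true QTc × RR^(a − b), with RR = 60 / heart rate. Assumed: true QTc 400 ms on Day 0 at 120 to 150 beats per minute, true QTc 460 ms on Day 5 at 105, and a between 0.30 and 0.42.

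Rise read with b = 0.5 when the true rise is 60 ms:

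| Day 0 rate | a = 0.30 | a = 1/3 | a = 0.42 |
|---|---|---|---|
| 120 | +55.0 | +56.0 | +58.3 |
| 130 | +47.6 | +50.0 | +55.5 |
| 140 | +40.6 | +44.3 | +53.0 |
| 150 | +34.0 | +39.0 | +50.6 |

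With b = 1/3 the same rise reads +59.3 to +61.5 at a Day 0 rate of 120 and +56.3 to +68.8 at 150.

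Absolute values with b = 0.5: the true 460 ms at 105 reads 514, 505 and 481 ms for a = 0.30, 1/3 and 0.42. With a = 1/3, the true 400 ms on Day 0 reads 400 × 0.5^(−1/6) = 449 ms at 120 and 400 × 0.4^(−1/6) = 466 ms at 150. So the printed exponent adds children to the absolute categories and removes them from the increase categories.

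**The case against.** The strongest reply is that the plan is silent here, not wrong. Several parts of it stand.

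- *A reader might infer that no 5-day v 3-day QTc comparison is planned.* The documents do not support that. ECGs are taken in both regimens for a safety purpose, and comparative safety is a secondary objective and outcome. The comparison is implied; its time point, contrast, interval and handling of repeat episodes are missing.
- *A reader might infer that the study has chosen an arm-mean-only analysis.* The more natural reading of the triplicate sentence is data reduction: three tracings averaged to one value per child and visit. That is a sound per-child variable and does not prevent counting. The central-tendency label leaves the point open, and no sentence commits to the counts.
- *Adverse-event grading could catch outliers.* This is a partial safeguard. Sections 7 and 8 grade events per child but never mention QTc. Section 7.3 requires a form only for events that are grade 3 or higher and also serious or unexpected, and none for grades 1 and 2. That does not give a count by regimen with a denominator.
- *The formula sits in a background sentence and names Fridericia.* That is true, and a programmer who follows the name would use 1/3. But it is the only correction formula printed. The example is also at the margin: a true rise of exactly 60 ms does not exceed 60 even when computed correctly, and with a = 1/3 a true rise of 80 ms still reads +61 to +78.
- *Large QTc values are expected to be rare.* Section 6.10 reports none above 500 ms after baseline in children under 12, and 0.2% in adults. At 0.2%, the chance of at least one in 50 is 1 − 0.998^50, about 10%. This lowers the expected yield. It does not remove the reason to count in a regimen that Section 7.2 describes as under evaluation.

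**Conclusion.** The point holds as a gap in specification. The thresholds are cited and not adopted, the implied regimen comparison has no method, and the one printed formula carries the wrong exponent for the correction it names. A mean-only report would comply and could hide a 4% outlier rate behind a 2.8 ms shift. The 0.5 exponent, if used, would distort both kinds of threshold count in opposite directions.

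The sizes rest on assumed SDs, heart rates and QT-RR exponents; at a Day 0 rate of 120 the understatement of a 60 ms rise is small (it reads +55 to +58). A reader might infer that 5-day AL prolongs QTc, or that prolongation will be missed. Nothing in the documents shows either; missed prolongation is only possible. Nor do the documents show that Bazett's correction is intended: the separate glossary entries and the use of QTcF point to a misprint.

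This should be fixed before analysis. It concerns a secondary safety subset and does not touch the primary PK or recurrence outcomes.

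**What to change.** In Section 6.10 and Section 9:

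1. Using the triplicate mean per child and visit, tabulate by regimen the numbers with QTcF above 450, 480 and 500 ms and with rises from Day 0 above 30 and 60 ms, with exact 95% intervals, beside the mean.
2. Compare regimens on end-of-treatment QTcF (Day 3 or Day 5), adjusted for Day 0 QTcF and allowing for children with ECGs in more than one episode. Show the intensive (4 to 6 hour) and population (8 to 12 hour) ECGs separately as well as pooled.
3. Correct the exponent in Section 6.10 to 1/3.

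Two additions are optional. One is a sensitivity analysis of within-child rises against the Day 28-or-later ECG, leaving out children with recurrence or retreatment by then and not used to compare regimens. The other is a statement of precision beside the safety conclusion: zero of 50 excludes only rates above about 6% one-sided or 7% two-sided.

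The cost is a little more analysis and a one-term correction. Every ECG needed is already scheduled and no sample size changes.
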